### **Screening**

1. Medical history (including any HIV resistance testing) and physical examination
2. Labs: CBC-D, CD4, creatinine, phosphorus, albumin, ALT, bilirubin, lipids, CD4, HIV RNA, HBsAg (if last result was negative > 6 mo ago), anti-HCV (if last result was negative > 6 mo ago), UPCR, UACR, DEXA hip and spine
3. Add HBV DNA, HBeAg and anti-HBe for all known to be HBsAg+ (if last result was > 3 mo ago)

4. Add HCV RNA for all known to be anti-HCV+, if last test was negative > 12 months ago
5. Add FibroScan for all HCV RNA+ and/or HBsAg+
6. EFV related symptom scores

Any labs performed for standard of care within 30 days of screening visit will be considered baseline results and used to determine inclusion/exclusion criteria.

### **Study Intervention**

Randomized 1:1, double-blind treatment with ATP and placebo for B/F/TAF (control arm) or B/F/TAF and placebo for ATP (experimental arm). Study medication (two tabs, one active, one placebo) will be taken once daily at the same time of day and with the same amount of food (or not) that the patient was doing when taking ATP prior to study entry. Patients will take double-blinded study medications for 52 weeks, but the primary efficacy analysis will be based on treatment week (TW) 48 data.

At TW52, patients will be told whether they were taking ATP or B/F/TAF, and offered the option of continuing on B/F/TAF, if they were assigned to that arm, or switching to B/F/TAF if they were in the control group receiving ATP. Gilead will supply B/F/TAF to patients after TW52 until B/F/TAF is covered by the provincial formulary.

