B/F/TAF (bictegravir/FTC/TAF) is an investigational STR that contains neither TDF nor Efv. B/F/TAF includes TAF and FTC, which are well characterized and approved drugs, and FTC/TAF is arguably the best dual nucleoside backbone currently available (IAS-USA 2016 Guidelines), combined with an investigational ISTI, bictegravir, which does not require a pharmacoenhancer, has minimal drug interactions (Custodio J. CROI 2017), has a very high genetic barrier to resistance (Tsiang M, et al. AAC 2016) and was potent and well tolerated in a phase 2 clinical trial (Sax P, et al. Lancet HIV 2017;4:e154-60) and 4 phase 3 clinical trials. B/F/TAF is smaller in size than ATP and the 3 currently approved STRs containing ISTIs. Four phase 3 trials of B/F/TAF met criteria for virologic non inferiority at 48 weeks of treatment, all of which have been published. In particular, B/F/TAF has significantly fewer side effects than dolutegravir-containing regimens, and no treatment-emergent resistance has been reported in any patient receiving B/F/TAF to date.

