### **Study Design**

Randomized, double-blind, placebo-controlled comparison of the efficacy and safety of switching to B/F/TAF or remaining on ATP in HIV+ adults who have been receiving ATP for > 2 years with virologic suppression. After a 52-week period of blinded study therapy, participants will be offered open-label B/F/TAF until it is covered by the provincial drug plan.

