### **Stopping criteria**

- Investigator determines it is not safe for individual to continue study treatment (including but not limited to intercurrent illness or participant noncompliance)
- Lack of study drug efficacy
  - o >100 copies/mL for two consecutive tests
- Pregnancy
- Participant request for any reason
- Discontinuation of study by Health Canada or Research Ethics Board

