### **Analysis**

The primary analysis will be the difference between baseline and week 48 in urine albumin/creatinine ratio (UACR) between ATP and B/F/TAF treated participants. Safety and tolerability will also be assessed.

Eight secondary statistical analyses will be performed comparing the ATP and B/F/TAF arms of the study:

- (1) HIV-1 RNA < 50 copies/mL at TW48

- (2) Differences from baseline to TW4 in EFV symptom scores (as per GS-US-292-0109)
- (3) Differences from baseline to TW48 in urine protein/creatinine ratio (UPCR)
- (4) Differences from baseline to TW48 in estimated glomerular filtration rate (eGFR)
- (5) Differences from baseline to TW48 in bone mineral density (BMD) at the hip
- (6) Differences from baseline to TW48 in BMD at the spine
- (7) Differences from baseline to TW48 in CD4 lymphocyte counts
- (8) Differences from baseline to TW48 in serum lipids

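### Does calling the week 48 analysis the primary efficacy analysis leave the primary endpoint unclear, or leave the trial unable to show maintained suppression?

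*Protocol*

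**What the plan says.** The Study Design section describes a "comparison of the efficacy and safety of switching to B/F/TAF or remaining on ATP". The Study Intervention section sets 52 weeks of blinded treatment and adds, "but the primary efficacy analysis will be based on treatment week (TW) 48 data". No endpoint is attached to that clause.

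The Analysis section is specific: "The primary analysis will be the difference between baseline and week 48 in urine albumin/creatinine ratio (UACR) between ATP and B/F/TAF treated participants". It then says "Eight secondary statistical analyses will be performed comparing the ATP and B/F/TAF arms of the study", and item (1) of that list is "HIV-1 RNA < 50 copies/mL at TW48". No hypothesis, test, confidence level or margin is given for that item. The other seven items are changes from baseline.

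Two other places bear on how to read the word efficacy. Under Stopping criteria, lack of efficacy is defined virologically, as ">100 copies/mL for two consecutive tests". The Background section reports, "Four phase 3 trials of B/F/TAF met criteria for virologic non inferiority at 48 weeks of treatment". Sample Size gives 100 patients per arm and no other design input.

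**The concern.** There are two worries.

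The first is about the label. Stopping criteria uses efficacy in the virologic sense, so a reader could take the primary efficacy analysis in Study Intervention to mean HIV-1 RNA. The Analysis section makes the primary endpoint a renal marker. Background presents kidney disease as a harm of one component of ATP, so UACR looks more like a toxicity outcome than an efficacy one. If the primary endpoint were truly open, either UACR or HIV-1 RNA could later be presented as the main result.

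The second is about inference. Everyone enters with HIV-1 RNA below 50 copies/mL, so the efficacy question in a switch study is whether suppression is kept. The Analysis section speaks only of comparing the arms. If that became an ordinary test of difference between two proportions near 100%, and a non-significant result were taken as reassurance, a clinically relevant loss of suppression could pass as no difference.

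**Working it through.** **Which endpoint is primary**

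| Section | Time point | Endpoint named | Status |
|---|---|---|---|
| Study Intervention | week 48 | none | called primary efficacy |
| Analysis, first sentence | week 48 | change in UACR | primary |
| Analysis, list item (1) | week 48 | HIV-1 RNA below 50 copies/mL | secondary |

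The time points agree. Only the Analysis section assigns endpoints, and it gives HIV-1 RNA an explicit secondary status. The Study Intervention clause explains why treatment runs to week 52 while the analysis uses week 48. It does not name a second primary endpoint.

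**How much a plain difference test could miss**

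The protocol gives no response rate, margin, significance level or power, so there is no stated figure to reproduce beyond 100 per arm. The rates and margins below are assumptions, tests are two-sided at 5%, and no dropout is allowed for. Differences are B/F/TAF minus ATP.

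*Example A: 97/100 against 90/100.*
- Fisher exact p = 0.082.
- The Newcombe interval combines the Wilson limits of each arm: 82.6% to 94.5% for 90/100, and 91.5% to 99.0% for 97/100.
- Lower limit: −0.07 − √[(0.900 − 0.8256)² + (0.9897 − 0.970)²] = −0.147.
- Upper limit: −0.07 + √[(0.9448 − 0.900)² + (0.970 − 0.9155)²] = +0.0005.
- The interval is −14.7 to +0.05 points.
- The Wald interval is −0.07 ± 1.96 × √(0.97×0.03/100 + 0.90×0.10/100) = −0.07 ± 1.96 × 0.0345, that is −13.8 to −0.2 points. It excludes zero, so this example is borderline and depends on the method.

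*Example B: 95/100 against 86/100.*
- Fisher exact p = 0.051.
- The Newcombe interval is −17.6 to −0.7 points, which excludes zero. An analyst reporting this interval would report a loss of suppression, so the example does not illustrate a missed one.

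*Power of a difference test.* For true rates of 97% and 92%, exact Fisher power with 100 per arm is 23%. For 95% and 90%, the normal-approximation power is 27%.

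**What the same sample supports as a non-inferiority comparison**

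Power = Φ(margin / √[2p(1 − p)/100] − 1.96), with the same true rate p in both arms.

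- p = 0.97: standard error √(2×0.97×0.03/100) = 0.0241. A 10-point margin gives Φ(0.10/0.0241 − 1.96) = Φ(2.19) = 98.6%.
- p = 0.95: standard error √(2×0.95×0.05/100) = 0.0308. A 10-point margin gives Φ(0.10/0.0308 − 1.96) = Φ(1.28) = 90%.

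| True rate, both arms | 4 points | 8 points | 10 points |
|---|---|---|---|
| 95% | 25% | 74% | 90% |
| 97% | 38% | 91% | 98.6% |

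A difference test is weak here. An interval for the same data, read against a margin near 10 points, is not. The wording of the Analysis section permits either.

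**The case for a change.** The strongest argument for a change is that the primary endpoint belongs in the protocol, and a SAP should not have to settle it. Stopping criteria gives efficacy a virologic meaning, so on the protocol's own vocabulary Study Intervention points to HIV-1 RNA while Analysis points to UACR. The mismatch in wording stands. The supposed consequence does not, because the Analysis section leaves no room to choose: UACR is primary and HIV-1 RNA is numbered among the secondary analyses. The Analysis section also mentions safety and tolerability separately from UACR, so the protocol does not itself file UACR under safety. Loose wording for the UACR analysis is the likelier reading.

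The second argument is that the Background section already uses non-inferiority language, so the plan should have carried it over. That passage says the earlier trials "met criteria for virologic non inferiority at 48 weeks of treatment". It describes those trials and does not set the framework for this one. The rationale given here is mainly the renal, bone and neuropsychiatric toxicity of ATP, which fits a renal primary endpoint with virologic outcome secondary.

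What stands is a caution about reading: a non-significant difference with 100 per arm would not establish maintained suppression. The protocol does not say that it would. It specifies no difference test and no rule for interpreting non-significance. A confidence interval for the difference in proportions is also a comparison of the arms.

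**Conclusion.** No change to the plan is needed. The label in Study Intervention is a clerical slip. Correcting it would alter no endpoint, time point, sample size or result, because the Analysis section is explicit and both sections use week 48.

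The missing hypothesis, interval method and margin for HIV-1 RNA are details of a secondary endpoint that a SAP commonly supplies, and that SAP is not available here. Nothing in the protocol prevents a sound choice. An analyst would report the difference in proportions with its 95% interval, and would either judge it against a clinically justified margin fixed before unblinding or present it as descriptive, without claiming maintained suppression.

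On the assumptions stated (equal true rates, no dropout), 100 per arm gives about 90% power for a 10-point margin at 95% suppression, and 91% to 98.6% for 8 to 10 points at 97%. At 95%, an 8-point margin has only 74% power. A margin must rest on clinical grounds rather than on what the sample can support, and the protocol offers no basis for one. The figures show how a non-significant result should be read. They do not show an error in what the protocol fixes.

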### **Study Flow and Monitoring after Screening**

Patients whose screening lab tests are satisfactory will return within 30 days to initiate double-blinded study therapy. Repeat lab testing will not be done on the day that blinded study therapy is initiated.

Blood will be collected at TW4 ( $\pm$  7 days), TW12 ( $\pm$  30 days), TW24 ( $\pm$  30 days), TW36 ( $\pm$  30 days), and TW48 ( $\pm$  7 days) for HIV RNA.. CD4 and phosphorus will be measured at TW24 and TW48. Lipids will be done at TW48. Creatinine, ALT, and albumin will be measured at TW12, TW24, TW36 and TW48. Urine tests will be done at TW24 and TW48. Samples will be discarded once analyzed and will not be stored for future use. DEXA will be done at TW48. EFV-related symptom scores will be done at TW4.

Physical exams will be completed if needed based on symptoms. Adverse events will be assessed and treatment adherence discussed. Serious adverse events will be collected and reported to Gilead Sciences, Inc and Health Canada. In women of childbearing potential, highly effective birth control is required and pregnancy testing will be performed. Visits will be performed in clinic, via telehealth, or via telephone.

Concomitant medications will be recorded. Prescription drug therapy for osteoporosis is not allowed at enrollment. Antacids (e.g., Tums or Rolaids), the ulcer medication sucralfate, and vitamin or mineral supplements that contain calcium, iron, or zinc are to be taken at least 2 hours before or 2 hours after study drug.

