### **Breaking the Blind**

In the event of a medical emergency, the investigator will be able to obtain treatment assignment of each participant.

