### **Safety Analysis**

Investigator will review data and safety information annually including adverse events, efficacy lab results, and safety lab results.

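### Does telling each participant their arm at their own week 52 of treatment, while others are still blinded, undermine the comparison?

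*Protocol*

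**What the plan says.** The Study Intervention section fixes two times: "Patients will take double-blinded study medications for 52 weeks, but the primary efficacy analysis will be based on treatment week (TW) 48 data". It then sets the planned disclosure: "At TW52, patients will be told whether they were taking ATP or B/F/TAF, and offered the option of continuing on B/F/TAF". The Study Design section agrees: "After a 52-week period of blinded study therapy, participants will be offered open-label B/F/TAF until it is covered by the provincial drug plan". Neither section ties disclosure to database lock, to the last participant's visit, or to completion of that participant's own records.

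The other rule on opening codes is under Breaking the Blind: "In the event of a medical emergency, the investigator will be able to obtain treatment assignment of each participant".

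On safety, the Study Flow and Monitoring section says "Adverse events will be assessed and treatment adherence discussed" without tying this to particular weeks, and visits may be in clinic, by telehealth or by telephone. The Analysis section adds "Safety and tolerability will also be assessed". The Safety Analysis section says "Investigator will review data and safety information annually including adverse events, efficacy lab results, and safety lab results". Under Stopping criteria, the investigator has discretion: "Investigator determines it is not safe for individual to continue study treatment (including but not limited to intercurrent illness or participant noncompliance".

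**The concern.** In a blinded trial, codes are usually protected until the data that depend on judgement are settled. Here they open on each participant's own clock. If enrolment is staggered, staff may learn the arms of early completers while later participants are still being followed. The investigator, who can stop treatment and reviews accumulating data each year, could then form impressions by arm. Query handling and late analysis choices could also be made by people who know some allocations.

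A second part does not depend on accrual. Blinded treatment runs to week 52, but the last scheduled assessments are at week 48. Adverse events from the final four weeks might first be reported at the contact where the arm is disclosed. Participants had taken the control drug for more than 2 years before entry, so learning the arm could colour what they report and how staff attribute it. Safety and tolerability are to be assessed, and a participant cannot be blinded again.

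**Working it through.** **When each endpoint is due, compared with disclosure at week 52** (Study Flow and Monitoring; Analysis)

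| Endpoint | Due | Type |
|---|---|---|
| UACR (primary) | week 48 | laboratory |
| HIV-1 RNA below 50 copies/mL | week 48 | laboratory |
| UPCR, eGFR, CD4 count, lipids | week 48 | laboratory |
| BMD at hip, BMD at spine | week 48 | DEXA |
| Efavirenz symptom scores | week 4 | participant report |

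The week 48 blood window is ±7 days, so blood is drawn between weeks 47 and 49. The gap to disclosure is 52 − 49 = 3 weeks to 52 − 47 = 5 weeks. No window is given for urine or DEXA, but both are scheduled at week 48. The symptom score, the one listed endpoint that rests on self-report, is due 52 − 4 = 48 weeks before disclosure.

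**The part that does not depend on accrual**

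Blinded weeks after week 48: 52 − 48 = 4. Share of blinded exposure: 4/52 = 7.7%, or 200 × 4 = 800 of 200 × 52 = 10,400 participant-weeks if all 200 complete.

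**The part that depends on accrual**

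The protocol gives no accrual period. Assume even entry at week t over A weeks. The first code opens at calendar week 52.

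- Week 48 visits still due then are those with t > 4: share (A − 4)/A.
- Blinded exposure still to come then (A ≤ 52) averages A/2 weeks of 52: share A/104.
- After 20 of 200 codes, at week 52 + 0.1A, it averages (0.9A)²/(2A) = 0.405A weeks: share 0.405A/52.

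| A (assumed) | Week 48 visits still due | Blinded exposure left, first code | Blinded exposure left, 20 codes |
|---|---|---|---|
| 4 | 0% | 4% | 3% |
| 26 | 22/26 = 85% (169 of 200) | 25% | 20% |
| 52 | 48/52 = 92% (185 of 200) | 50% | 41% |

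These figures show how much blinded follow-up runs while some other participants' arms are known. They are not shares of biased outcomes: a completer's code does not reveal the arm of someone still taking two tablets, one active and one placebo.

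**What deferral would cost**

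If codes waited for the last week 48 visit, at calendar week A + 48, the first participant enrolled would wait (A + 48) − 52 = A − 4 weeks longer: 22 weeks at A = 26, 48 at A = 52 and 74 at A = 78, plus time to lock the database.

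**Do the sections conflict?**

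Breaking the Blind gives the investigator emergency access; it does not say that codes may be opened in no other case. Study Intervention covers planned disclosure at the end of blinded treatment. The two rules serve different purposes and are compatible. No section gives codes to outcome assessors or analysts, and the Safety Analysis section does not say that the annual review is by arm.

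**The case for a change.** The strongest case for a change is that the protocol itself fixes when arms are disclosed, so that part cannot be put down to an analysis plan that is not shown. Staggered entry is also likely. The Background names one regional program with about 316 patients on the control drug; if that is the source, which is an inference, 200 participants are 200/316 = 63% of the pool, and enrolling them within 4 weeks is implausible. Adverse events rest on report and judgement and may be collected by telephone. A sentence requiring them to be recorded before disclosure would cost almost nothing, and the 3 to 5 weeks after the week 48 blood draw leave time to settle the data.

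Much of this stands as description: disclosure is individual, no condition on the data is written, and the order of events at week 52 is not stated. The step to harm does not stand. That late adverse events are first heard at the disclosure contact is a possibility, since adverse-event assessment is not tied to a given week. Asking about events before telling someone their arm is what staff would ordinarily do. The route from completers' arms to decisions about participants who are still blinded is conjecture. Custody of codes, data freeze and blinding of analysts are matters that a protocol commonly leaves to the analysis plan or a data-handling plan.

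**Conclusion.** No change to the plan is needed. Followed as written, it collects every listed endpoint before the participant's own disclosure, and all but the week 4 symptom score are laboratory or DEXA measures. The remaining exposure is the unstated order of adverse-event recording in the last 4 blinded weeks, 7.7% of blinded exposure, which staff can be expected to settle sensibly.

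Holding all codes to the end of the trial would be a trade-off with a poor return. It would add about 22 to 74 weeks of waiting for the first participants, under assumed accrual of 26 to 78 weeks. It would also clash with the week 52 offer, which is worded differently for each arm: continuing for one, switching for the other. No benefit to an endpoint has been shown to set against that.

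This conclusion assumes that week 48 urine and DEXA are done near their scheduled time, and that codes are handled outside the protocol in the usual way. It does not depend on the accrual period.

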### **Study Flow and Monitoring after Screening**

Patients whose screening lab tests are satisfactory will return within 30 days to initiate double-blinded study therapy. Repeat lab testing will not be done on the day that blinded study therapy is initiated.

Blood will be collected at TW4 ( $\pm$  7 days), TW12 ( $\pm$  30 days), TW24 ( $\pm$  30 days), TW36 ( $\pm$  30 days), and TW48 ( $\pm$  7 days) for HIV RNA.. CD4 and phosphorus will be measured at TW24 and TW48. Lipids will be done at TW48. Creatinine, ALT, and albumin will be measured at TW12, TW24, TW36 and TW48. Urine tests will be done at TW24 and TW48. Samples will be discarded once analyzed and will not be stored for future use. DEXA will be done at TW48. EFV-related symptom scores will be done at TW4.

Physical exams will be completed if needed based on symptoms. Adverse events will be assessed and treatment adherence discussed. Serious adverse events will be collected and reported to Gilead Sciences, Inc and Health Canada. In women of childbearing potential, highly effective birth control is required and pregnancy testing will be performed. Visits will be performed in clinic, via telehealth, or via telephone.

Concomitant medications will be recorded. Prescription drug therapy for osteoporosis is not allowed at enrollment. Antacids (e.g., Tums or Rolaids), the ulcer medication sucralfate, and vitamin or mineral supplements that contain calcium, iron, or zinc are to be taken at least 2 hours before or 2 hours after study drug.

### **Stopping criteria**

- Investigator determines it is not safe for individual to continue study treatment (including but not limited to intercurrent illness or participant noncompliance)
- Lack of study drug efficacy
  - o >100 copies/mL for two consecutive tests
- Pregnancy
- Participant request for any reason
- Discontinuation of study by Health Canada or Research Ethics Board

### **SAE definition (from Health Canada)**

*A serious adverse event (experience) or reaction is any untoward medical occurrence that at any dose:*

- results in death,
- is life-threatening,

NOTE: The term "life-threatening" in the definition of "serious" refers to an event in which the patient was at risk of death at the time of the event; it does not refer to an event which hypothetically might have caused death if it were more severe.

- requires inpatient hospitalisation or prolongation of existing hospitalisation,
- results in persistent or significant disability/incapacity, or
- is a congenital anomaly/birth defect.

Medical and scientific judgement should be exercised in deciding whether expedited reporting is appropriate in other situations, such as important medical events that may not be immediately life-threatening or result in death or hospitalisation but may jeopardise the patient or may require intervention to prevent one of the other outcomes listed in the definition above. *These should also usually be considered serious.* Examples of such events are intensive treatment in an emergency room or at home for allergic bronchospasm; blood dyscrasias or convulsions that do not result in hospitalisation; or development of drug dependency or drug abuse

